1. DESIGN

Design overview

Cardiac murmurs in children: Predictive value of cardiac markers (CAMUS) is an observational study on spontaneously discovered cardiac murmurs in children. The primary aim is to establish the predictive value of cardiac markers for identification of cardiac disease in children with heart murmurs. NT-proBNP and hs-troponins are considered the most relevant cardiac markers. Secondary aims are: a) To establish age-adjusted reference range for cardiac markers in children, and b) To explore aspects of cardiovascular physiology in children.

In part 1 of the project, a total of ~500 individuals aged 4 weeks to 10 years will be consecutively recruited among those referred to the Dept. of Paediatrics and Adolescent Medicine, Akershus University Hospital (Ahus) for assessment of heart murmurs. The protocolized investigational program of the study includes clinical examination, symptom assessment, pulse oximetry, blood sampling, ECG recording, and echocardiography. A definite diagnosis of cardiac disease or not will be based upon the echocardiographic examination, hence serving as the “gold standard”.

In part 2 of the project, a total of ~125 individuals aged 4 weeks to 10 years with confirmed congenital heart disease (CHD) and scheduled for intervention at OUS Rikshospitalet will be included. They will undergo the same investigational program as in part 1. A main purpose of part 2 is to validate the prediction model developed in part 1.

Table 1. Criteria for inclusion and exclusion

Inclusion criteria	Exclusion criteria
Spontaneously discovered heart murmur at general practitioner's office (part 1)	Known cardiac disease (part 1 only)
Confirmed cardiac anomaly and scheduled for intervention at OUS Rikshospitalet (part 2)	Other chronic or acute disorder (part 1 only)
Age > 4 weeks, < 10 years	Medications (part 1 only)

2. ENDPOINT

Outcome variable

The primary outcome variable in part 1 is a diagnosis of cardiac disease based upon echocardiographic assessment. The diagnostic process will adhere to international consensus guidelines on paediatric cardiology (Doshi & Chikkabryappa, 2018; Sachdeva et al., 2020; Writing Committee et al., 2021). Thereafter, all participants will be assigned to either of two groups: a) A cardiac diagnosis that needs intervention/treatment and/or further clinical follow-up (cases); b) No cardiac diagnosis or a cardiac

Cardiac murmurs in children: Predictive value of cardiac markers (CAMUS)

diagnosis that does not need intervention/treatment and/or further clinical follow-up (controls). Hence, the primary outcome variable is dichotomous. The assignment to cases vs. controls will follow pre-defined criteria pertaining to each cardiac diagnosis/diagnostic group (Table 2).

In part 2, all participants are assigned as cases, as per the inclusion criterium of a confirmed cardiac anomaly in need of intervention.

Table 2. Criteria for assignment of cases (need of intervention and/or clinical follow-up) vs. controls (no need of intervention nor clinical follow-up)	
Primary cardiac diagnosis	Criteria for caseness (only one criterium needs to be fulfilled per diagnosis)
Persistent foramen ovale (PFO)	N/A (never assigned as case)
Atrial septal defect (ASD), all subgroups	Case if: 
 - Ostium premium defect - Sinus venosus defect - Ostium secundum defect diameter > 3 mm OR with signs of right atrium volume load.
Persistent ductus arteriosus (PDA)	Case if: 
 - Ductus diameter >1.5 mm. - LA/Ao ratio >1.5 - Retrograde diastolic flow in the abdominal aorta. - Continuous murmur
Ventricular septum defect (VSD), all subgroups	Case if 
 - Perimembranous location - Inlet location - Subpulmonary outlet/supracristal location - Muscular location with diameter >5 mm OR left ventricular dilatation OR Qp/Qs ≥1.5. - Multiple defects
Aortic valve pathology (stenosis (AS), regurgitation (AR), bicuspid valve)	Case if: 
 - Flow velocity ≥ 2.0 m/s. - Hypertrophy of left ventricle. - Aortic regurgitation (more than trivial)
Pulmonary valve pathology (stenosis (PS), regurgitation (PR))	Case if: 
 - Flow velocity ≥ 2.5 m/s (valvular, subvalvular or supravalvular) - More than a trivial regurgitant jet (vena contracta < 2 mm) with dilatation of right ventricle OR diastolic flow reversal in the main pulmonary artery OR rapid flow deceleration during the entire diastole OR pressure half time < 100 ms.
Mitral valve pathology (stenosis (MS), regurgitation (MR))	Case if: 
 - MS: dilatation of left atrium with pressure half time of E wave > 140 ms OR mean pressure gradient > 5 mm Hg. - MR: 
 o More than a small central jet filling more than 20 % of left atrium. OR eccentric jet reaching the posterior wall of left atrium. o Dilatation of left atrium and left ventricle OR pulmonary vein systolic flow reversal. o Other structural/functional abnormalities of the mitral apparatus (leaflet prolapse, leaflet split, etc.)
Tricuspid valve pathology (stenosis (TS), regurgitation (TR))	Case if: 
 - TS defined as mean pressure gradient > 5 mmHg AND pressure half time >190 ms. - TR with dilatation of right atrium OR flow velocity > 2.8 m/s
Peripheral pulmonary stenosis (PPS)	Case if: 
 - Flow velocity > 2.5 m/s.
Coarctation of the aorta (CoA)	Case if: 
 - Flow velocity ≥ 2.0 m/s AND diastolic continuation of flow across the suspected coarctation region. - Abdominal aorta doppler pattern with low systolic waveform amplitude and antegrade diastolic flow.

Cardiac murmurs in children: Predictive value of cardiac markers (CAMUS)

	- Presence of posterior shelf as sign of ductal tissue involvement in aortic wall
Complex congenital heart disease	N/A (always assigned as case)
Cardiomyopathies, all subgroups	N/A (always assigned as case)

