3. OTHER VARIABLES

The main analysis is aimed to construct a prediction model for CHD that can be applied in general practice. The analysis will entail bivariate logistic regression between potential predictor (independent) variables and the primary outcome variable (cf. above), followed by multivariable logistic regression modelling and construction of receiver operating curves (ROC).

Relevant predictor (independent) variables include (but are not restricted to):

- *Background*: Sex, age, ethnicity, weight/height
- *Clinical symptoms*: Breathlessness, exertion intolerance/low physical fitness, sweating, reduced general condition
- *Routine clinical findings*: Heart rate, respiratory rate, SaO₂, murmur characteristics, blood haemoglobin,
- *ECG characteristics*: PR interval, QRS interval, QRS axis, Sokolow-index
- *Blood biomarkers*: NT-proBNP, troponin T, hsCRP, IL-6

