4. SAMPLE SIZE CONSIDERATIONS

The value of possible predictors will be assessed through the construction of Receiver Operating Characteristics (ROC) curves, and calculation of negative predictive value. Based upon register data from the outpatient clinical at Ahus, the prevalence of cardiac disorder in the population under study is estimated at 2 %. The area under the ROC-curve for NT-proBNP in a previous study with similar methodology has been established at 0.85 (Law et al, 2009). The possible clinical application of the results from the present study requires a very low risk of false negatives (ie. no patients with cardiac disorders should be deemed healthy based upon a certain cardiac marker). Therefore, the level of significance (α) is set to 0.01. Given a test power ($1 - \beta$) = 0.8, sample size is estimated at 400 patients. A drop-out rate of up to 20 % might be assumed (technical problems, refusal of blood sampling, etc), therefore a total of 500 patients should be included in the study.

In part 2, when a population of 125 patients with well-defined CHD is added to the population of about 500 individuals previously recruited, the ratio of cases:controls increases to about 0.25. This will enable an α -value less than 1×10^{-10} , and a power ($1 - \beta$) of comparable magnitude, which we find satisfactory.

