6. STATISTICAL METHODS

General considerations

Continuous variables will be reported with parametric (mean/standard deviation) or non-parametric (median, quartiles) descriptive statistics, depending on the distribution. Ordinal/nominal variables will be reported as frequency tabulation. All statistical tests will be carried out two-sided. A p-value ≤ 0.05 is considered statistically significant throughout.

Predictor analysis

In part 1, the relationship between each potential predictor variable and the primary outcome variable will first be explored in univariate logistic regression analyses. Collinearity between predictor variables will be assessed by correlation analyses, and dimensionality reduction by PCA will eventually be considered. Then, all variables with a p-value ≤ 0.25 in the univariable analyses will be included in the first modelling step. In order to obtain a more parsimonious model, the combination of variables that gives the lowest Akaike Information Criteria (AIC) will constitute the final model. The value of predictor(s) in the final multivariable model will be assessed through the construction of Receiver Operating Characteristics (ROC) curves, and calculation of negative predictive value.

In part 2, the prediction model from part one will be validated by including a total of n~125 individuals with known CHD in the study population. The prediction model should correctly classify all these cases; if not, the model will be adjusted. We aim for zero false negatives, i.e. all cases with cardiac abnormalities in need of intervention and/or hospital follow-up should be identified. To explore the potential of the prediction model to classify all cases based upon this premise, we will apply different combinations of levels of the identified predictor variables.

Cross-sectional analyses

For the secondary study aims, cross-sectional analyses across cases and controls are feasible. Such analyses will feature parametric tests (Student t), non-parametric tests (Mann-Whitney), regression analyses or table analyses (Chi-square, Fisher) as appropriate.

Sensitivity analyses

Throughout, sensitivity analyses applying a different classification of caseness in the primary outcome variable will be carried out:

1. Caseness defined as all abnormalities identified by echocardiography, independent of intervention/follow-up needs
2. Caseness defined as all abnormalities in need of surgical or catheter-based intervention

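### In part 1 a child with PDA can be a case through a continuous murmur alone while murmur characteristics are a candidate predictor, and no planned analysis isolates this possible overlap

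*SAP*

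**What the plan says.** SAP Section 2 works in two steps. Echocardiography gives the diagnosis. Then: "Thereafter, all participants will be assigned to either of two groups", according to Table 2. The table header states that "only one criterium needs to be fulfilled per diagnosis". The PDA row has four separate items. Three are echocardiographic (ductal diameter, LA/Ao ratio, retrograde diastolic flow in the abdominal aorta). The fourth is "Continuous murmur", a finding on auscultation.

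Section 3 lists "murmur characteristics" under routine clinical findings as a candidate predictor of the same outcome. Section 6 selects predictors in two stages: "all variables with a p-value ≤ 0.25 in the univariable analyses will be included in the first modelling step", and then "the combination of variables that gives the lowest Akaike Information Criteria (AIC) will constitute the final model". It has no rule for a predictor that also helps to define the outcome.

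Section 6 plans two sensitivity analyses. The first counts every echocardiographic abnormality as a case. The second counts only abnormalities that need surgical or catheter-based intervention. For the second cohort, Section 2 says: "In part 2, all participants are assigned as cases".

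**The concern.** Take a part 1 child whose PDA meets none of the three echocardiographic items but who has a continuous murmur. The murmur makes the child a case, and the same murmur may then be offered to the model as a predictor of being a case. For such a child, agreement between predictor and outcome arises by construction and is no evidence that the murmur predicts disease.

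What is at stake is the murmur term in the multivariable model intended for general practice: whether it is selected, and how much it appears to add. With few expected cases in part 1, each one carries weight. No planned analysis would show how far a murmur term depends on these children.

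**Working it through.** **Expected number of cases.** Section 4 says that "the prevalence of cardiac disorder in the population under study is estimated at 2" per cent, with 400 evaluable and 500 recruited children. The figure of 400 reproduces with AUC 0.85 against 0.5 (the null value is my assumption), two-sided alpha 0.01, power 0.80, 49 controls per case and the Hanley-McNeil variance:

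(2.576 × √0.0850 + 0.842 × √0.0589)² / 0.35² = 7.45, rounded up to 8 cases; 8/0.02 = 400; 400/0.80 = 500.

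So part 1 should yield 0.02 × 400 = 8 to 0.02 × 500 = 10 cases.

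**Assumptions the SAP does not settle.** k is the number of part 1 children who are cases by the murmur item alone, and m is the number of controls with a continuous murmur. I take k = 1 and a yes/no continuous-murmur term. With k = 0 everything below is nil.

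**Effect on AUC, k = 1.**
- Murmur term alone, (sensitivity + specificity)/2, no other case positive and specificity near 1: gain 1/(2 × 10) = 0.050 to 1/(2 × 8) = 0.063, from about 0.50.
- Model at 0.85, if this child outranks every control: (9 × 0.85 + 1)/10 = 0.865 and (7 × 0.85 + 1)/8 = 0.869, a rise of at most 0.015 to 0.019.
- Hanley-McNeil standard error at 0.85, with Q1 = 0.85/1.15 = 0.7391 and Q2 = 2 × 0.7225/1.85 = 0.7811. For 10 cases and 490 controls: √[(0.1275 + 9 × 0.0166 + 489 × 0.0586)/4900] = 0.077. For 8 and 392: 0.086.
- If the 125 part 2 cases are pooled with 10: 0.15/135 = 0.001.

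**Effect on univariable selection, N = 500.** For a of n cases and m controls with the murmur, LR = 2[ℓ(a, a+m) + ℓ(n−a, N−a−m) − ℓ(n, N)], where ℓ(x, t) = x ln(x/t) + (t−x) ln(1−x/t). The change in AIC is 2 − LR. Example with a = 1, m = 1, n = 10: 2(−1.386 − 45.038 + 49.019) = 5.19, so p = 0.023 and AIC changes by −3.19.

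| Other cases with the murmur | m | Child as case: LR p, AIC change | Child as control: LR p, AIC change |
|---|---|---|---|
| 0 | 1 | 0.023, −3.19 | 0.79, +1.93 |
| 0 | 7 | 0.142, −0.15 | 0.59, +1.71 |
| 0 | 8 | 0.164, +0.06 | not selected |
| 1 | 1 | selected | 0.036, −2.39 |
| 1 | 3 | selected | 0.070, −1.27 |
| 1 | 7 | selected | 0.144, −0.13 |

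Here m excludes the child. In the control column the child is an extra positive control and 9 cases remain.

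With no other positive case, the child's label decides selection for m = 1 to 7. The Wald p-values, 0.006 at m = 1 and 0.069 at m = 7, also pass the screen. At m = 0 there is separation: the likelihood-ratio p is 0.005, but the Wald p is about 0.999 and fails the screen. The SAP does not name the test.

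With one other positive case and m = 1 to 7, the term is selected whichever way the child is labelled. At m = 8 the same formula gives −4.32 as case and +0.06 as control, so this result is confined to that range.

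**Planned analyses set against the overlap.** Sensitivity definition 1 makes every PDA a case, and definition 2 counts only need of intervention. Neither uses the murmur item. Both also move other diagnoses: under definition 1, for example, persistent foramen ovale becomes a case. A changed result could therefore not be traced to the murmur item. Part 2 adds only cases, assigned by its inclusion criterion, so it cannot show the effect either.

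**The case against.** Need for follow-up may properly depend on a clinical finding, and echocardiography must still show the duct. That stands, and the case definition is not disputed here.

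The SAP does not say that the murmur predictor includes a continuous/not-continuous item, how it is coded, or whose auscultation counts for Table 2. That stands too: the two may be the same observation, but the text does not establish it. With a multi-level murmur variable the calculations above would not apply as they are.

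A reader might infer that the overlap runs through every planned analysis. It does not, because both sensitivity definitions abandon the murmur criterion. What they fail to do is isolate it.

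A reader might also infer that a single such child decides whether the murmur enters the model. That needs particular conditions, chiefly that no other case has a continuous murmur and that about 1 to 7 controls do. Sensitivity to one child is in any case common to any rare binary predictor when only 8 to 10 cases are expected. It comes from the few events and is not peculiar to this overlap.

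**Conclusion.** The concern holds in a narrow form. One item for one diagnosis lets a clinical sign define caseness while murmur characteristics are also candidate predictors, and no planned analysis separates out the consequence.

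The size depends on k, which the SAP does not give. It is nil if k = 0, or if the continuous feature is not coded or not retained. With k = 1, the bound on the model AUC is about a fifth of its standard error (0.015/0.077 and 0.019/0.086). The selection results are univariable; selection in the multivariable model would also depend on the other terms.

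A reader might conclude that the primary aim is compromised. The SAP does not support that: the murmur does not enter the AUCs of NT-proBNP and troponin taken alone, so they are not inflated by it. The change below is worth making because it is cheap, and it is optional.

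**What to change.** Keep the primary case definition and the list of candidate predictors. Report k, the number of part 1 children who are cases through the continuous-murmur item alone. Add to the sensitivity analyses in Section 6:

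*3. If any part 1 child is a case through the continuous-murmur item alone, repeat the primary analysis with PDA caseness based only on the echocardiographic items in Table 2.*

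The cost is one line, one reported count and at most one further analysis. If k = 0, reporting it closes the question. No child changes group and no predictor is lost in the primary analysis. Which criterion defines need for follow-up stays with the investigators.

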3. OTHER VARIABLES

The main analysis is aimed to construct a prediction model for CHD that can be applied in general practice. The analysis will entail bivariate logistic regression between potential predictor (independent) variables and the primary outcome variable (cf. above), followed by multivariable logistic regression modelling and construction of receiver operating curves (ROC).

Relevant predictor (independent) variables include (but are not restricted to):

- *Background*: Sex, age, ethnicity, weight/height
- *Clinical symptoms*: Breathlessness, exertion intolerance/low physical fitness, sweating, reduced general condition
- *Routine clinical findings*: Heart rate, respiratory rate, SaO₂, murmur characteristics, blood haemoglobin,
- *ECG characteristics*: PR interval, QRS interval, QRS axis, Sokolow-index
- *Blood biomarkers*: NT-proBNP, troponin T, hsCRP, IL-6

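### No planned analysis shows whether the general-practice and zero-false-negative conclusions depend on murmur characteristics that appear to be recorded in hospital

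*SAP*

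**What the plan says.** Section 3 gives the purpose of the main analysis: "The main analysis is aimed to construct a prediction model for CHD that can be applied in general practice". Its list of candidate predictors includes, under routine clinical findings, "murmur characteristics, blood haemoglobin".

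Section 1 sets out where the data arise. Part 1 children are "consecutively recruited among those referred to the Dept. of Paediatrics and Adolescent Medicine, Akershus University Hospital (Ahus) for assessment of heart murmurs". On the examinations, it states: "The protocolized investigational program of the study includes clinical examination, symptom assessment, pulse oximetry, blood sampling, ECG recording, and echocardiography". For part 2, in children awaiting intervention at a second hospital, it adds: "They will undergo the same investigational program as in part 1". The general practitioner (GP) appears in Table 1 only as the place where the murmur was discovered.

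Section 6 selects variables by univariable p-value and then by AIC, and assesses the final model by ROC curve and negative predictive value (NPV). It then adds the part 2 cases and adjusts the model if any are misclassified. The target is explicit: "We aim for zero false negatives, i.e. all cases with cardiac abnormalities in need of intervention and/or hospital follow-up should be identified". The two sensitivity analyses change the definition of a case. Neither changes the set of predictors.

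**The concern.** NT-proBNP, oxygen saturation and haemoglobin are measured values and should mean much the same wherever they are taken. The character of a murmur is a judgement by whoever is listening. Every part 1 child already has a murmur, so its presence carries little information; what could separate cases from controls is how it is described.

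If that description comes from hospital examiners, its weight and the model's cut-off are fitted to hospital auscultation. A GP who hears a pathological murmur as innocent would then lower the score of a true case, possibly below the cut-off. That is the error the plan wants to exclude. Part 2 repeats the hospital programme, so it would not reveal the loss. The report could state a zero-false-negative result for general practice without showing whether it rests on hospital auscultation.

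**Working it through.** **What the SAP fixes.**

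| Item | Setting in the SAP |
|---|---|
| Intended use (section 3) | General practice |
| Examination, part 1 (section 1) | Programme for children referred to a hospital department |
| Examination, part 2 (section 1) | Same programme, children awaiting intervention at a second hospital |
| Who records the murmur | Not stated; no GP recording described |
| Sensitivity analyses (section 6) | Case definition only |

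**Inputs for an illustration.** The SAP gives no figure for auscultation accuracy. Its only usable number is the AUC of 0.85 for NT-proBNP (section 4). I assume:
- a binormal marker;
- one yes/no murmur sign, independent of the marker given disease status;
- hospital sensitivity/specificity of 80/80, 85/85 or 90/90%;
- GP accuracy of 60/60, 70/70 or 80/80%, always below the hospital's.

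The section 4 sample size of 400 is not affected by this point.

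**Formulas.** Marker separation: d = √2 × z(0.85) = 1.466. Score = marker log-likelihood ratio + murmur log-likelihood ratio at hospital accuracy. The cut is set so that hospital sensitivity equals a target. Let a and b be the probabilities that a case exceeds the cut when the murmur is read as pathological or as innocent. If the GP's murmur sensitivity is s, rule sensitivity = s·a + (1 − s)·b. The loss is therefore (hospital s − GP s) × (a − b).

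**Worked example**, hospital 90/90%, GP 60/60%:
- Cut at 99%: a = 1.000, b = 0.900. Hospital: 0.9 × 1.000 + 0.1 × 0.900 = 0.990. GP: 0.6 × 1.000 + 0.4 × 0.900 = 0.960.
- Cut at 95%: a = 0.9988, b = 0.5111. Hospital: 0.9 × 0.9988 + 0.1 × 0.5111 = 0.950. GP: 0.6 × 0.9988 + 0.4 × 0.5111 = 0.804.

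**Rule sensitivity with GP readings (%)**

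| Hospital | GP | Cut at 95% | Cut at 99% | Cut at 99.9% |
|---|---|---|---|---|
| 80/80 | 70/70 | 92.7 | 98.5 | 99.8 |
| 80/80 | 60/60 | 90.4 | 98.0 | 99.8 |
| 85/85 | 80/80 | 93.4 | 98.7 | 99.9 |
| 85/85 | 70/70 | 90.2 | 98.0 | 99.8 |
| 85/85 | 60/60 | 87.1 | 97.3 | 99.7 |
| 90/90 | 80/80 | 90.1 | 98.0 | 99.8 |
| 90/90 | 70/70 | 85.2 | 97.0 | 99.7 |
| 90/90 | 60/60 | 80.4 | 96.0 | 99.6 |

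**Discrimination.** AUC is 0.92-0.96 with hospital readings and 0.79-0.92 with GP readings. With the cut at 95%, specificity is 64-84% with hospital readings and 51-75% with GP readings. The marker alone at 95% sensitivity has specificity Φ(1.466 − 1.645) = 43% in either setting.

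**If GPs over-call.** Only the GP's murmur sensitivity enters the formula, so rule sensitivity falls only if that is below the hospital's. With hospital 85/85% and a cut at 95%, a GP at 90% sensitivity and 60% specificity gives 96.6%. A GP at 95% and 50% gives about 98%. The cost is then specificity.

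**Why NPV alone is a weak signal.** At 2% prevalence (section 4), take the 95% cut, hospital 90/90% and GP 60/60%. Hospital NPV = 0.98 × 0.838 / (0.98 × 0.838 + 0.02 × 0.050) = 0.9988. GP NPV = 0.98 × 0.579 / (0.98 × 0.579 + 0.02 × 0.196) = 0.9931. Sensitivity has fallen by about 15 points and NPV by 0.6.

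**The case against.** The strongest reply is that this is the ordinary transportability caveat of any rule derived in hospital, and that it rests on a chain of conditions. The SAP does not say who records murmur characteristics, and the protocol may. Murmur is one of many candidates and must survive selection with appreciable weight. GPs must then under-call and not over-call. Symptoms such as reduced general condition also depend on the assessor, so dropping murmur does not by itself make the model valid for GPs. Murmur is also available to every GP and can still help: with GP accuracy of 70-80%, AUC in the illustration is 0.86-0.92, against 0.85 for the marker alone.

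Most of this stands, and it limits the point. A reader might infer that the SAP states that hospital staff record the murmur; it does not, although the examination it describes makes that likely. A reader might take 80-93% as the expected sensitivity in general practice. That range belongs to a 95% cut and assumed accuracies, and the plan aims for zero misses; at cuts nearer that aim the loss is about 0.3 to 3 points (99%) or below 0.4 (99.9%). A reader might also infer that murmur must be removed from any model meant for GPs. That is a debatable trade-off which the documents do not settle.

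The reply does not remove the gap. The intended setting, the candidate list, the selection steps and the sensitivity analyses are all fixed in the SAP, and none of them shows how far the conclusion depends on this predictor.

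**Conclusion.** The point holds as a conditional one. A model intended for general practice may include an observer-dependent predictor that appears to be recorded only in hospital. If it does, and GPs detect pathological murmurs less often, sensitivity can fall without any planned analysis showing it. The size is unknown: about 96-99% at a 99% hospital cut and 80-93% at a 95% cut, with no loss of sensitivity if GPs over-call. These figures rest on assumed accuracies, a binormal marker and conditional independence; only the AUC of 0.85 comes from the SAP. The documents do not show that the model will fail in general practice, nor that murmur will enter it. What is missing is a cheap check on what the study may conclude.

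**What to change.** In section 6, add a pre-specified sensitivity analysis that repeats the same model-building steps and the part 2 check without murmur characteristics. Report AUC, sensitivity, specificity and NPV for both versions; NPV alone would not be enough.

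State in advance how the result will be used. The general-practice and zero-false-negative conclusions are given without qualification only if the murmur-free version supports them. Otherwise the report says that they hold for hospital auscultation only. If murmur characteristics are not selected, the two versions should coincide and nothing changes. This run addresses murmur only; it does not establish that the remaining predictors transfer to general practice.

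Cost: one extra model run and a few sentences in the SAP, with no new data. The downside is a possibly less favourable specificity in the murmur-free version, or a narrower claim.

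### Symptom and murmur predictors are recorded in part 2 after the diagnosis is known, so part 2 sensitivity for a model that uses them may be misstated; report it with and without these items

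*SAP*

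**What the plan says.** Section 1 describes two groups. In part 1, "a total of ~500 individuals aged 4 weeks to 10 years will be consecutively recruited" after referral for a heart murmur, and Table 1 excludes children with known cardiac disease from this part only. Part 2 adds "a total of ~125 individuals aged 4 weeks to 10 years with confirmed congenital heart disease (CHD) and scheduled for intervention". Of the part 2 children the SAP says: "They will undergo the same investigational program as in part 1". That programme comprises "clinical examination, symptom assessment, pulse oximetry, blood sampling, ECG recording, and echocardiography".

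Section 2 fixes the outcome in part 2: "In part 2, all participants are assigned as cases, as per the inclusion criterium of a confirmed cardiac anomaly in need of intervention". All controls therefore come from part 1.

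Section 3 lists the candidate predictors. The symptom items are "Breathlessness, exertion intolerance/low physical fitness, sweating, reduced general condition", and murmur characteristics stand among the routine clinical findings. The same list holds heart rate, respiratory rate, SaO2, haemoglobin, ECG measures and blood biomarkers. It does not separate predictors that rest on judgement from those that are measured. The stated purpose is a model for use in general practice.

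Section 6 (Predictor analysis) builds the model in part 1 by univariate screening and AIC. It then validates the model by adding the part 2 children, requires all of them to be classified correctly, and adjusts the model if any is missed. Different combinations of predictor levels are to be tried in pursuit of zero false negatives.

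**The concern.** A symptom history or a description of a murmur depends on what the person giving or recording it already believes. In part 2 the family knows that the child has heart disease and awaits an intervention. In part 1 no cardiac disease is known at entry. The same programme may therefore not yield the same measurement in the two parts, and the difference coincides with case status.

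General practice resembles part 1: nobody has the diagnosis yet. If part 2 reporting is shaped by the diagnosis, part 2 sensitivity for a model with symptom or murmur items need not carry over to that setting. A result of zero false negatives could rest on these items without the reader being able to see it. Detection could also be credited to symptoms that the cardiac markers, which are the subject of the primary aim, did not achieve.

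**Working it through.** **Inputs.** Part 1: about 500 enrolled (Section 1), 400 evaluable after up to 20% drop-out (Section 4). Part 2: about 125, all cases (Sections 1 and 2). Expected prevalence of cardiac disorder in part 1: 2% (Section 4).

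**The plan's own figure.** Section 4 gives a case:control ratio of about 0.25 after part 2 is added. 125/500 = 0.25, so it reproduces. Counting the expected part 1 cases as cases gives (125 + 10)/(500 − 10) = 135/490 = 0.276, which is still of that order.

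**Share of pooled cases with a diagnosis known at entry.** Formula: 125 / (125 + prevalence × part 1 size).

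- 500 in part 1: 0.02 × 500 = 10 cases; 125/135 = 92.6%.
- 400 evaluable in part 1: 0.02 × 400 = 8 cases; 125/133 = 94.0%.
- The same 20% loss in both parts: 100/(100 + 8) = 92.6%.

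The corresponding share among controls is 0%, because part 2 supplies no control and part 1 excludes known disease.

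**Dependence on the prevalence.** Caseness under Table 2 need not equal the 2% register figure. With assumed values for 500 children in part 1:

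| Part 1 caseness (assumed) | Part 1 cases | Part 2 share of pooled cases |
|---|---|---|
| 1% | 5 | 125/130 = 96.2% |
| 3% | 15 | 125/140 = 89.3% |
| 5% | 25 | 125/150 = 83.3% |
| 10% | 50 | 125/175 = 71.4% |

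The share stays above 70% throughout.

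**Which analysis step is touched.** Screening and AIC selection use part 1 only, so part 2 reporting cannot affect which predictors enter the model. Validation and adjustment do use part 2 data. There, one child changes part 2 sensitivity by 1/125 = 0.8 percentage points. Because the target is zero false negatives, a single child whose classification turns on a symptom or murmur item decides whether the target is met.

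**Which predictors are touched.** The four symptom items and murmur characteristics are open to this. Blood markers, haemoglobin, SaO2 and ECG intervals are not.

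**The case against.** The strongest reply is that exposure to a possible bias is not bias. A reader might infer that the symptom and murmur items are inflated in 93% of cases. The SAP does not support that: 93% is the share of pooled cases whose diagnosis is known beforehand, and the document gives no effect of awareness.

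Nor does it support the reading that the error must flatter the model. Part 2 children are all scheduled for intervention, so more symptoms may simply reflect more severe disease. Medication is an exclusion in part 1 only, so some part 2 children may be treated and report fewer symptoms. A murmur is an entry condition in part 1 but not in part 2, so murmur items could do worse there. Part 1 families are not free of suspicion either, since their child was referred to hospital for a murmur.

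A reader might also compute a pooled association and conclude that an uninformative symptom would be selected. Suppose such a symptom is reported in 10% of part 1 children and, through awareness alone, in 20% of part 2 children (both assumed). Cases with the symptom number 0.20 × 125 + 0.10 × 10 = 26 of 135, and controls 49 of 490. The odds ratio is (26/109)/(49/441) = 2.15. At 30% it is (38.5/96.5)/(49/441) = 3.59. The arithmetic is right, but Section 6 selects predictors in part 1 alone, so these figures describe a selection step that is not planned.

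Finally, masking of the examiner may be set in the protocol, which is not at hand. Its absence from the SAP is no finding.

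All of this limits the claim. It does not remove it: masking an examiner leaves the family's own knowledge in place, and the part 2 data cannot separate severity from awareness. That inability is itself the reason why part 2 cannot cleanly validate these items.

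**Conclusion.** The point holds as a risk to the part 2 validation and adjustment, not as a demonstrated bias. On the SAP's own figures about 93% of pooled cases and no control have a diagnosis known before symptoms and murmur are recorded (71% to 96% for assumed part 1 caseness of 10% down to 1%). Part 2 sensitivity for a model containing these items may be misstated, by an amount and in a direction that the documents do not fix.

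The conclusion rests on three stated facts: diagnosis at entry in part 2, exclusion of known disease in part 1, and identical treatment of all predictors in Section 6. It matters only if the part 1 final model retains a symptom or murmur item, or if the adjustment step brings one in. It is a cheap improvement rather than a flaw that invalidates the plan.

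**What to change.** In Section 6, Predictor analysis:

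1. Keep the part 1 final model as the model that part 2 validates. Symptoms and murmur are what a general practitioner has to hand, so they should not be dropped from it.
2. Also fit in part 1, by the same selection procedure, a model restricted to objectively measured predictors (blood markers, ECG, SaO2, heart rate, respiratory rate). Background variables raise no such issue and can be handled alike in both models.
3. Report part 2 sensitivity and the number of false negatives for both models side by side.
4. State that coefficients and cut-offs of symptom and murmur items will not be re-estimated or re-tuned on part 2 data.
5. Claim zero false negatives without qualification only if it also holds in the objective-predictor model.

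The cost is SAP wording and one extra model fit on data already being collected. The downsides are a possibly less favourable validation figure and only limited part 2 evidence on the symptom items.
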